### 9.0 STATISTICAL PROCEDURES

#### 9.1 Randomization

Once informed consent has been obtained, eligible patients will be entered into the study randomly assigned to one of the selected treatment strategies in an interactive Web-based randomization session where exclusion and eligibility criteria will be assessed. Patients will be randomized to the time of administration (Day 3 or Day 7) using a variable block size of 4 or 6. Patients will be randomized to therapy type (active or control therapy), using variable block sizes of 3 or 6, randomly selected. Patients will be stratified by clinical center. When a patient is randomized, the clinic will be given an identification (ID) number and acrostic, specific information on the assigned treatment regimen, and a list of procedures to be completed at the baseline visit. A participantspecific schedule of visits and procedures will be displayed for printing locally. The DCC will monitor patient recruitment by providing reports to the Core Laboratories and Project Office (PO) as appropriate during the recruitment phase. Updated reports will be maintained on an Internet site accessible to all units of the study. The recruitment reports will provide data on recruitment of women and minorities (African-Americans, Hispanics, and Asians). Goals for recruitment will be set and will be reviewed by the DCC and PO.

### 9.2 Statistical Analysis

Biostatisticians at the DCC, with the assistance of scientific programmers, have adapted or developed a number of statistical programs for analyzing study data. Data are analyzed for both data monitoring purposes, as described above, and for the purpose of detecting beneficial or adverse treatment effects. The DCC uses standard statistical packages such as SAS, S-PLUS, R and Stata to perform statistical analyses.

### 9.3 Baseline Analyses

Although the stratified (by clinical center) random assignment of participants to the various treatments should ensure comparability with respect to known and unknown variables, imbalance may occur by chance. Descriptive statistics for baseline characteristics known or suspected to be associated with outcomes will be prepared for the various treatment groups. The variables considered in such a description can be categorized as follows: (1) demographic characteristics, (2) medical history, (3) physical examination, and (4) laboratory data. Exact testing for categorical variables and Student *t* testing for continuous variables will be used to evaluate the differences in baseline variables between treatment groups.

### 9.4 Analyses of Primary Outcome

### 9.4.1 Baseline evaluations

The compatibility of baseline characteristics between the two treatment groups will be ascertained using standard normal tests (including t-tests) for continuous variables and exact testing for categorical variables. All hypotheses testing, and all effect sizes and their 95% confidence intervals will be evaluated using the general linear mixed model for continuous outcome variables. For categorical outcomes, generalized linear mixed model will be used. Nonparametric techniques will also be used in the statistical analysis (39-41).

### 9.4.2 Co-primary endpoint evaluations

Each primary endpoint, global LVEF(%) and regional LV function is a continuous variable. General linear mixed modeling techniques will be utilized to assess the effect of treatment on the primary endpoint of the study. For patients recruited to the Day 3 arm of the study, the six month MRI will be compared to the Day 3 MRI. For patients recruited to the Day 7 treatment group, the six month MRI will be compared to the Day 7 MRI

The analysis variable will be the change in LVEF (either global or regional) from the immediate pre-infusion level to six months. Both unadjusted and adjusted treatment effects will be computed; adjustments will be for clinical site as well as for baseline covariates whose association with the dependent variable is generally accepted. In keeping with standard methodology for clinical trials, the primary analysis will compare the randomized study groups.

Despite the efforts of CCTRN Investigators to ensure that patients return to their center for follow-up evaluation, we anticipate that a small number of subjects will be unable to return for their follow-up endpoint assessment. Last observation carried forward analyses will be carried out as supportive evaluations.

Anticipating this difficulty, the sample size for this study has been increased by a small percent, allowing the Investigators to capture complete data on a number of patients as close to the pre-specified sample size as possible. However, for those patients who are missing the final six month endpoint data, we will carry out a Last Observation Carried Forward (LOCF) analysis. For a patient who is missing the follow up information, the value of the follow-up measure will be assumed to be equal to their base-line value. Thus the difference in the endpoint measure over the six month follow-up will be zero. While a large number of missing data points, corrected in this matter can produce a bias toward the null, this standard LOCF procedure will be adequate for the small number of patients with missing data.

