## 6.3 Day 3 or Day 7 (Study Product Infusion)

- Incremental medical history
- Physical Exam, including vital signs, height and weight
- Assessment of NYHA class (see Appendix 2)
- Bone marrow aspiration for stem cell harvest
- Study product infusion in catheterization laboratory
- Vital signs pre and post bone marrow harvest and cellular product infusion
- Troponin I or T, CK, CK-MB collected one time on the morning following infusion
- Telemetry after procedure (18-24hrs)
- Cardiac MRI (baseline) All patients undergo cardiac cMRI at Day 3 and those patients randomized to therapy on Day 7 will undergo repeat cMRI on Day 7 (send to MRI core lab following study product randomization)
- Five 10 ml venous blood (purple top tubes) for biorepository FACS and migration analysis
- 10 ml venous blood (green top heparin tubes) for biorepository plasma cryostorage
- Review of medications for changes
- Assess for AEs /serious adverse events (SAEs)

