### **8.0 ENDPOINT EVALUATION AND CLASSIFICATION**

A cardiac MR 1.5 T scanning unit (Avanto, Cardiac MR Scanner, Siemens Medical Systems or equivalent) will be used for cardiac MR images. The exact cMRI Scanner will vary at each institution, however, the exact imaging protocols will be established by the MRI Core Lab. cMRI was chosen by the Network to evaluate the primary and secondary endpoints because it is independent of the geometric assumptions required for calculations of ejection fraction compared to echocardiography or left-ventriculography. Furthermore, the inter-study reproducibility for cMRI is significantly better than echocardiography for measurements such as LVEF, LVEDV, LVESV and cardiac mass (36, 37). However, the patient's measurements of global LVEF from entry into the study until

completion will be assessed by echocardiography in place of cMRI when MRI is contraindicated.

A series of scout images will be required with a pulse sequence that collects an image in a fraction of the RR interval. Scout imaging will start with a transverse view at the mid-ventricular level. Using the first scout as a localizer, the technologist will acquire the next scout image for the image plane that intersects with the long axis of the LV. A horizontal long axis cine series (four chamber view) will be acquired first followed by the long axis cine (twp chamber view). The image planes for the short axis studies will start at the base of the heart, at least two cm above the mitral-tricuspid valve plane to achieve maximal LV coverage. Using Tru-FISP (balanced- FFE) cineangiography, the slices will be consecutively positioned every 7 mm from the base to apex with a 3 mm interslice gap. The acquisition window for retrospectively-triggered cine sequence will be obtained. End-expiratory breath-hold with sampling throughout the entire cardiac cycle will be employed because of better reproducibility of each slice position for more accurate left ventricular volume analysis. A minimum of 20 cardiac phases will be used to cover the RR interval. All patients will undergo baseline cMRI measurements at Day 3 given that resolution of myocardial stunning and improvement in global and regional LV function often continues to occur between Day 3 and Day 7 which would negatively bias the Day 7 group when LV function is reanalyzed at six months.

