### 9.4.3 Secondary analyses

Both the effect of cell administration and the effect of the timing of cell administration will be evaluated for each of the secondary endpoints. Using general linear model procedure, the effect of cell administration on LV mass, end diastolic volume, end systolic volume, and infarct size will be assessed. The analysis variable will be the change in LVEF (either global or regional) from the immediate pre-infusion level to six months. Both unadjusted and adjusted treatment effects will be computed; adjustments will be for baseline covariates whose association with the dependent variable is generally accepted. Logistic regression will be used to assess the effect of cell administration on the combined endpoint of death, reinfarction, repeat revascularization, and hospitalization for HF.

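### Section 9.4.2 takes the Day 7 arm's change from a Day 7 scan although section 8.0 calls that biased, so spontaneous recovery enters the active-only timing comparison

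*Protocol*

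**What the plan says.** The protocol fixes the baseline of the co-primary endpoints in two incompatible ways.

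- **Section 8.0** sets one baseline day for all: "All patients will undergo baseline cMRI measurements at Day 3". Its reason is that resolution of stunning and functional improvement often go on between Day 3 and Day 7, "which would negatively bias the Day 7 group when LV function is reanalyzed at six months".
- **Section 9.4.2** sets arm-specific baselines. The rule for the early arm is: "For patients recruited to the Day 3 arm of the study, the six month MRI will be compared to the Day 3 MRI". The late arm is given a different reference scan: "For patients recruited to the Day 7 treatment group, the six month MRI will be compared to the Day 7 MRI". It defines the analysis variable as the "change in LVEF (either global or regional) from the immediate pre-infusion level to six months".
- **Section 9.4.3** repeats the phrase "from the immediate pre-infusion level to six months" for the secondary analyses. The sentence still names LVEF, although the endpoints there are LV mass, volumes and infarct size.
- **Section 6.3** schedules both scans: "All patients undergo cardiac cMRI at Day 3 and those patients randomized to therapy on Day 7 will undergo repeat cMRI on Day 7".

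Timing is one of the two primary objectives (section 1.1). Section 3.2.6.2 evaluates it by comparing the active Day 7 group with the active Day 3 group. Its justification is that placebo patients respond alike whichever day they are infused.

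**The concern.** Under section 9.4.2 the Day 7 arm's change leaves out whatever recovery occurs between the two scans, while the Day 3 arm's change includes it. Section 8.0 describes exactly this bias and gives it as the reason for a common Day 3 scan.

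The premise of section 3.2.6.2 then fails on the protocol's own reasoning. With arm-specific baselines, Day 7 placebo patients would also show a smaller change than Day 3 placebo patients, so placebo response is not the same at both times. Because the planned contrast uses active patients only, nothing subtracts that difference. The trial could report a timing effect when there is none, or miss a real advantage of Day 7.

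**Working it through.** **Inputs from the protocol**

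- Two-sided alpha 0.05 (3.2.6.1); power 80% and 5% loss (Tables 5 and 6).
- Global LVEF: difference 5, SD 7 (3.2.6.2.1). Regional LVEF: difference 6.5, SD 10 (3.2.6.2.2).
- 40 active patients per time point, so 40 × 0.95 = 38 evaluable. 20 placebo patients per time point (Table 4), so 19 evaluable.

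**Assumption.** The protocol gives no size for the mean Day 3 to Day 7 recovery. Call it b, and take b = 1, 2 or 3 points.

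**Step 1: reproduce the stated sample sizes.** Equation (1) with k = 1:

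- Global: 4 × 7² × (1.960 + 0.842)² / (0.95 × 5²) = 64.8, i.e. 65.
- Regional: 4 × 10² × (1.960 + 0.842)² / (0.95 × 6.5²) = 78.2, i.e. 79.

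The t-test version gives 66.9 and 80.3, which match the stated 67 and 80. The sizing arithmetic is sound, and it is for the active-only contrast.

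**Step 2: what each contrast estimates.** Let B be mean LVEF at Day 3, M the mean six-month value on placebo, and e3 and e7 the cell effects at each time. Under section 9.4.2 the mean changes are:

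| | Day 3 arm | Day 7 arm |
|---|---|---|
| Active | M + e3 − B | M + e7 − B − b |
| Placebo | M − B | M − B − b |

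- Active Day 7 minus active Day 3: (e7 − e3) − b. Biased by the whole of b.
- Treatment-by-timing interaction: e7 − e3. Unbiased.
- Pooled active minus pooled placebo: both groups are half Day 3 and half Day 7, so b/2 is removed from each and cancels. The result is (e3 + e7)/2, which is unbiased.
- Active-only contrast with Day 3 as baseline in both arms: e7 − e3. Unbiased.

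**Step 3: error rate of the active-only contrast when e7 = e3.** SE = SD × √(2/38), which is 1.606 (global) and 2.294 (regional). Rejection probability = Φ(−1.96 + b/SE) + Φ(−1.96 − b/SE).

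| b | Global | Regional |
|---|---|---|
| 0 | 5.0% | 5.0% |
| 1 | 9.5% | 7.2% |
| 2 | 23.8% | 14.1% |
| 3 | 46.3% | 25.8% |

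**Step 4: power when Day 7 is truly better.** Power = Φ((δ − b)/SE − 1.96).

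| b | Global, δ = 5 | Regional, δ = 6.5 |
|---|---|---|
| 0 | 87.6% | 80.9% |
| 1 | 70.2% | 66.9% |
| 2 | 46.3% | 50.1% |
| 3 | 23.7% | 33.2% |

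If Day 3 were truly better by 5 points in global LVEF, power would rise to 96.2%, 99.2% or 99.9%. The distortion runs one way, against Day 7.

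**Step 5: power of the interaction.** SE = SD × √(2/38 + 2/19) = 2.782 (global) and 3.974 (regional).

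- Global: Φ(5/2.782 − 1.96) = 43.6%.
- Regional: Φ(6.5/3.974 − 1.96) = 37.3%.

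For 80% power at 2:1 allocation with 5% loss, about 292 (global) and 352 (regional) patients in total would be needed, against 120 planned.

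**The case against.** The strongest reply is that timing may be meant as an interaction. Sections 1.1 and 3.2.1 speak of timing influencing the cell effect, section 3.2.6.2.1 of a difference in treatment effect, and section 3.2.3 of an interaction for the secondary endpoints. Section 9.4.2 names mixed models without specifying an active-only contrast, and placebo patients are randomised at both times. On that reading the recovery cancels. This stands as a condition: the error rates above apply only to the active-only contrast. It does not rescue the plan, because section 3.2.6.2 defines that contrast, the sample size is built on it, and the interaction has under half power against the stated 80% basis.

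A second reply is that a pre-infusion baseline is usual practice. It is sound for cells against placebo at the same time point, but not for comparing active groups across time points.

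Third, the size of b is assumed. Section 8.0 says only that improvement often continues. That is why a range is shown, and the regional endpoint is less affected than the global one.

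A reader might also infer that the MVO and LVEF subgroups are compromised. The protocol does not say which scan defines them, and Day 3 values exist for everyone, so nothing on that is stated wrongly. Nor does the background clearly favour Day 7. Sections 2.1.2 and 2.1.3.6 lean towards later delivery, while section 2.1.3.2 reports homing factors and animal cell retention that favour earlier delivery.

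**Conclusion.** The contradiction between sections 8.0 and 9.4.2 is real, and as written it biases the timing comparison, which is a primary objective. The bias equals the mean recovery between the two scans. For assumed recoveries of 1 to 3 points, the nominal 5% error rises to between 9.5% and 46% (global) and between 7% and 26% (regional). Power for a true 5-point Day 7 advantage in global LVEF falls from 88% to between 70% and 24%. These figures rest on the protocol's SDs, 38 evaluable patients per arm, a normal approximation and the active-only contrast. The interval between scans is nominally four days, but section 4.3 allows infusion on Days 2 to 4 and Days 6 to 8, so the real gap varies.

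A reader might conclude that the overall cell effect is biased too. It is not, in expectation: allocation is 2:1 within each time point, so the arm-specific baselines fall on active and placebo patients in the same proportion.

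**What to change.** In section 9.4.2, and in the matching wording of 9.4.3, define the analysis variable for the timing comparison as the six-month cMRI minus the Day 3 cMRI in both arms. Keep change from the immediate pre-infusion scan as a sensitivity analysis. Reconcile sections 6.3, 8.0 and 9.4.2 so that they name the same baseline, and settle this before any outcome data are seen.

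If the SD of change from Day 3 is the assumed 7 (global) and 10 (regional), the stated sample sizes stand, with 87.6% and 80.9% power at 38 per arm. If the interaction is what is intended, say so and report its power.

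The cost is small but not wording alone. The Day 3 cMRI is already scheduled for every patient, but section 4.3 permits infusion on Day 2, and a Day 3 scan in such a patient would follow the infusion. The protocol must state how the baseline scan is ordered relative to infusion for these patients. A scan moved to Day 2 would bring back a smaller baseline mismatch, so their number should be reported.

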#### 3.2.6.1 Assumptions

In the absence of efficacy monitoring by the DSMB, hypothesis testing for the primary endpoint(s) will be carried out at the 0.05 level. Assuming independence and normality of the observations, the sample size is calculated using the normal approximation to the two sample *t*-test statistic

$$N = \frac{\left(k+1\right)\sigma_{\Delta}^{2}\left(\frac{k+1}{k}\right)\left[Z_{1-\alpha/2} - Z_{\beta}\right]^{2}}{\left(1-f\right)\delta^{2}}$$
(1)

where

January 25, 2010

- N = number of placebo patients + number of active group patients
- $\alpha$  = Type I error
- $\beta$  = Type II error
- $Z_c$  = the  $c^{th}$  percentile from the standard normal probability distribution
- $\delta$  = effect size (i.e., difference between the change in the active group over time minus the change in the control group over time
- $\sigma_{\Delta}^2$  = variance in the change over time (incorporates the correlation over time). This variance is pooled between the active and placebo groups.
- k = ratio of number of active group to placebo group patients.
- f = expected proportion of patients anticipated to be lost to follow-up.

In the analysis, the first examination will be the effect of cells on the co-primary endpoints, followed by an assessment of the influence of cell timing delivery on the relationship between cell therapy and the co-primary endpoints. Overall efficacy will be evaluated by comparing treatment versus control together. A sample size of 120 patients is required

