## 3.2.6.3.1 Effect of BMMNC infusion on global ejection fraction

Assume 80 active group patients and 40 control patients. We are assuming an absolute change  $\delta = 5$  and common group standard deviation of the difference of LVEF over time as  $\sigma(\Delta)_{LVEF} = 7$ , Type I error (two-tailed) = 0.0495. We anticipate that 5% of patients will be lost to follow-up. The standard deviation of the change in ejection fraction from baseline to six months is 7.0. These assumptions are based on the findings from the Wollert (24), Lunde (17), Schächinger (20), and Janssens (16) articles. Under these assumptions, the power is 94.9. A table displaying the sensitivity of the power computation to assumptions concerning treatment effect and standard deviation of the difference is provided (Table 7).

		Treatment Effect (δ)				
		4	5	6	7	8
Std Dev	5	0.981	0.999	1.000	1.000	1.000
of Diff	6	0.919	0.987	0.999	1.000	1.000
(σ)	7	0.820	0.949	0.991	0.999	1.000
	8	0.711	0.882	0.965	0.993	0.999

Table 7. Power for the effect of dose on lobal Ejection Fraction
Type I error = 0.05; N=120; 2:1 active:placebo ratio followup losses = 5%

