#### 2.) The investigation of Assmus

Assmus et al (9) injected 245 million unfractionated autologous BMMNC (7.3 x 10^6 CD34 + /CD45+) suspended in 10 ml of X vivo-10 medium in 10 patients four days following successful primary PTCA/stenting for an AMI. At 4-month follow-up, LVEF by angiography improved from 52 to 61% and end-systolic volume decreased from 55 to 34 ml and mean tracer uptake by fluoro-deoxyglucose positron emission tomography (FDG-PET) increased in five of seven patients. At one and two year follow-up in 29 patients (11) LVEF had further improved by cardiac MRI and no evidence of infarct expansion was observed. Importantly, there was a positive correlation between EF at baseline and improvement in LVEF such that those with the most depressed ejection fractions posted the greatest gain in LVEF following stem cell therapy. No complications were reported with the intracoronary administration of the cells and no increase in C-reactive protein or troponin-I was observed.

There was one death reported in the treatment group due to sub-acute stent thrombosis that was unrelated to the therapy. No incidents of ventricular arrhythmias occurred and the authors reported that the high-pressure infusion of the stem cells though the PTCA catheter had no affect on cell viability or motility. However, the effect of brief occlusions and reperfusion on the myocardium during BMMNC infusion was not addressed.

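### Section 9.4.2 plans an unadjusted and an adjusted effect for each co-primary without saying which decides, and does not name the pre-infusion value as a covariate

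*Protocol*

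**What the plan says.** **Endpoint.** Section 9.4.2 fixes the outcome as a change score: "The analysis variable will be the change in LVEF (either global or regional) from the immediate pre-infusion level to six months". General linear mixed models are to be used.

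**Two estimates.** The same section continues: "Both unadjusted and adjusted treatment effects will be computed; adjustments will be for clinical site as well as for baseline covariates". The covariates meant are those with a generally accepted association with the outcome; none is listed. The one sentence about the primary analysis says that it compares the randomized groups. That identifies the comparison, not the model.

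**Other analyses.** Section 9.4.2 labels the last-observation-carried-forward analysis supportive. Section 9.4.1 adds, without a rank: "Nonparametric techniques will also be used in the statistical analysis".

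**Secondary endpoints.** Section 9.4.3 repeats the adjustment sentence without clinical site: "adjustments will be for baseline covariates whose association with the dependent variable is generally accepted". Sections 3.2.5 and 9.1 stratify randomization by clinical center.

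**Design basis.** Section 3.2.6.1 says that "the sample size is calculated using the normal approximation to the two sample"-sample t statistic, applied to changes without covariates, and that "hypothesis testing for the primary endpoint(s) will be carried out at the 0.05 level".

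**The concern.** Two estimates of the same effect will be produced for each co-primary endpoint. They are highly correlated but not identical, so one can cross 0.05 when the other does not. A protocol that plans both should say beforehand which one counts. Section 3.2.6.4 declines a familywise correction and relies on a small number of primary endpoints instead. Leaving two eligible results per endpoint weakens that safeguard.

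The second issue is precision. An unadjusted change score fixes the slope of the six-month value on the baseline value at 1. If the true slope is below 1, this wastes information and lets part of any chance baseline imbalance into the estimate. The pre-infusion cMRI is collected anyway (section 6.3), so using it costs nothing. Omitting site from the secondary models leaves the stratification factor out of the analysis, and no reason is given.

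**Working it through.** **1. Reproduce the stated power.** Inputs from sections 3.2.6.3.1 and 3.2.6.3.2: 80 active and 40 placebo patients with 5% loss, so 76 and 38; global δ = 5, SD of change 7; regional δ = 6.5, SD 10. Power = Φ(δ / (SD·√(1/n₁ + 1/n₂)) − z).

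- Global: the standard error is 7·√(1/76 + 1/38) = 1.391 and 5/1.391 = 3.595. Power is Φ(3.595 − 1.960) = 94.9%, as stated.
- Regional: the standard error is 1.987 and 6.5/1.987 = 3.272. Power is 90.5% at 0.05, as in Table 8, and 90.45% at 0.0495 (text: 90.4%).
- Regional timing comparison, 38 versus 38 active patients (section 3.2.6.2): the standard error is 10·√(2/38) = 2.294 and 6.5/2.294 = 2.833. Power is 80.9%.

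The power text uses "Type I error (two-tailed) = 0.0495" while section 3.2.6.1 and the table headings use 0.05. The difference is immaterial here (94.90% against 94.85% for the global endpoint).

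**2. Effect of adjusting for baseline.** The protocol gives the SD of change but not the correlation between visits. With visit SDs s₀ and s₁, r = (s₀² + s₁² − 49)/(2·s₀·s₁), residual variance = s₁²(1 − r²), and slope = r·s₁/s₀.

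| s₀ / s₁ | Source | r | Residual SD | Change in variance | Slope | Global power, δ = 5 |
|---|---|---|---|---|---|---|
| 8 / 8 | assumed | 0.617 | 6.29 | −19.1% | 0.617 | 97.9% |
| 10 / 10 | assumed | 0.755 | 6.56 | −12.2% | 0.755 | 97.0% |
| 10 / 12.5 | Appendix 1, BOOST cell arm | 0.829 | 6.99 | −0.3% | 1.036 | 94.95% |

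The last row combines one arm of an earlier trial with this protocol's planned SD of change, so it is illustrative.

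If the same proportional reduction holds for regional function, the SD of 10 becomes 8.99 or 9.37. Regional timing power then rises from 80.9% to 88.3% or 85.6%. Under 10 / 12.5 it is 81.0%.

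**3. Chance baseline imbalance.** The 95% limit of imbalance is 1.96·s₀·√(1/76 + 1/38), which is 3.1 points for s₀ = 8 and 3.9 for s₀ = 10. The unadjusted effect moves by (slope − 1) × imbalance.

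- 8 / 8: 0.383 × 3.1 = 1.2 points at the limit, 0.6 at one standard error.
- 10 / 10: 0.245 × 3.9 = 1.0 points at the limit, 0.5 at one standard error.
- 10 / 12.5: 0.036 × 3.9 = 0.14 points at the limit.

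**4. Error rate if either test may count.** Under the null, the unadjusted and adjusted statistics are taken as bivariate normal with correlation √(1 − R²), where R² is the share of variance in change explained by the covariates. The chance that at least one passes 1.96 in absolute value is 6.0% for R² = 0.05, 6.6% for 0.12 and 7.0% for 0.19. Each test alone keeps its 5%.

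**The case against.** **Baseline LVEF may already be in the adjusted model.** A reader might infer from section 9.4.2 that it is excluded. The text does not support that: the open covariate class can include it, and a statistical analysis plan may list it. What stands is that the protocol does not name it.

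**The change score is not itself the fault.** A linear model of change with baseline as a covariate gives the same treatment effect as one of the six-month value. The criticism of a fixed slope applies only to the unadjusted estimate.

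**The protocol hints at an answer.** The sample size rests on an unadjusted comparison. Section 9.4.1 puts hypothesis testing for continuous outcomes in the general linear mixed model, and its nonparametric sentence cites the references that section 9.5 attaches to a separate substudy. This narrows the rivals, but does not choose between unadjusted and adjusted. Since section 9.4.2 does rank the carried-forward analysis, leaving these two unranked is a gap in what is stated, not detail held over.

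**The error inflation is conditional.** No passage allows a claim on either test. Chance imbalance is already part of the SD of change, so the unadjusted test alone keeps its level.

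**The Appendix 1 evidence is limited.** For the second non-randomized study the protocol says "there was a positive correlation between EF at baseline and improvement in LVEF", yet explains that the lowest starting values gained most, which is the opposite direction. Those patients all received cells. The REPAIR-AMI summary reports more benefit over placebo at low LVEF, which is effect modification, and LVEF is already a planned subgroup. Neither shows how change depends on baseline in untreated patients.

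**The precision gain is not assured.** This is correct: it rests on assumed SDs and disappears with 10 and 12.5.

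**Conclusion.** The point holds as a free improvement. The protocol commits to two estimates per co-primary and names neither as deciding. The pre-infusion value is unnamed as a covariate, and site is missing from the secondary adjustment.

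The 6–7% error rate per endpoint applies only if either result could be claimed, which the text neither permits nor excludes. The variance reduction of 12–19% assumes equal visit SDs of 8 to 10; the range extends down to nil with the Appendix 1 figures, without harm.

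A reader might infer that the trial is underpowered without adjustment. It is not: the overall comparison already has 94.9% and 90.4% power. The regional timing comparison, at 80.9%, has more room to gain, reaching about 86–88% if the same proportional reduction applies to regional function.

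**What to change.** **Co-primary endpoints.** In section 9.4.2, name one deciding model for each: a linear model of the change (or, equivalently, of the six-month value) on therapy and timing, with the pre-infusion cMRI value of the same endpoint and clinical site as covariates. For the timing question, add the therapy-by-timing term or the contrast between the two active arms, and say which. The timing term is needed because section 9.4.2 reads the pre-infusion value on Day 3 or Day 7 according to arm. Section 8.0 describes a Day 3 baseline for all patients, so the two sections should be reconciled at the same time.

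**Supportive analyses.** Label the unadjusted and any nonparametric results supportive. The carried-forward analysis already is.

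**Secondary endpoints.** In section 9.4.3, use the same form for LV mass, end-diastolic and end-systolic volume and infarct size, each with its own baseline value, and restore clinical site. That section's analysis variable is currently the change in LVEF and should be the change in the endpoint concerned.

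**Cost.** Protocol or analysis-plan wording and a few degrees of freedom: one for baseline and, with five centers as fixed effects, four for site. No new data or patients are needed.
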